6.5.5 Management of Specific Adverse Events or Adverse Drug Reactions

The management of irAEs is described in Section 6.5.4.4.

6.6 Packaging and Labeling of the Investigational Medicinal Product

Avelumab is formulated as a 20 mg/mL solution and is supplied by the Sponsor in single-use glass vials, stoppered with a rubber septum and sealed with an aluminum polypropylene flip-off seal.

All IMPs will be packaged and labeled in accordance with all applicable regulatory requirements and Good Manufacturing Practice Guidelines. Avelumab will be packed in boxes each containing 1 vial. The information on the trial treatment will be in accordance with approved submission documents.

Oxaliplatin, 5-FU, and capecitabine, will be supplied by the study center or by the Sponsor, according to local laws and regulations.

6.7 Preparation, Handling, and Storage of the Investigational Medicinal Product

The contents of the avelumab vials are sterile and nonpyrogenic, and do not contain bacteriostatic preservatives. Any spills that occur should be cleaned up using the facility's standard cleanup procedures for biologic products.

Avelumab must be stored at CCI to CCI until use, with a temperature log maintained daily. All medication boxes supplied to each trial site must be stored carefully, safely, and separately from other drugs.

Avelumab stored at room temperature CCI or at elevated temperatures CCI for extended periods is subject to degradation. Avelumab must not be frozen. Rough shaking of avelumab must be avoided.

For application in this trial, avelumab must be diluted with 0.9% saline solution (sodium chloride injection). Detailed information on infusion bags and medical devices to be used for the preparation of the dilutions and subsequent administration will be provided in the IPMP.

Avelumab must not be used for any purpose other than the trial. The administration of avelumab to subjects who have not been enrolled into the trial is not covered by the trial insurance.

Any unused portion of the solution should be discarded in biohazard waste disposal with final disposal by accepted local and national standards of incineration.

Storage, handling, preparation, and disposal of IMP should be according to local institutional guidelines.

6.8 Investigational Medicinal Product Accountability

The Investigator is responsible for ensuring accountability for avelumab and maintenance chemotherapy, including reconciliation and maintenance of drug records.

- Upon receipt of trial treatment, the Investigator (or designee) will check for accurate delivery and acknowledge receipt by signing (or initialing) and dating the documentation provided by the Sponsor and returning it to the Sponsor. A copy will be retained for the Investigator Site File.
- The dispensing of the trial treatment will be carefully recorded on the appropriate drug accountability forms provided by the Sponsor and an accurate accounting will be available for verification by the clinical research associate (CRA) at each monitoring visit.
- Trial treatment accountability records will include:
 1. Confirmation of trial treatment delivery to the trial site

2. The inventory at the site of trial treatment provided by the Sponsor and prepared at the site
 3. The use of each dose by each subject
 4. The disposition of unused trial treatment
 5. Dates, quantities, batch numbers, expiry dates and (for trial treatment prepared at the site) formulation, as well as the subjects' trial numbers.
- The Investigator should maintain records that adequately document:
 1. That the subjects were provided the doses specified by the clinical trial protocol/amendment(s)
 2. That all trial treatment provided by the Sponsor was fully reconciled.

Unused trial treatment must not be discarded or used for any purpose other than the present trial. Any trial treatment that has been dispensed to a subject must not be re-dispensed to a different subject.

The CRA will periodically collect the trial treatment accountability forms and will check all returns (both unused and used containers) before authorizing their destruction by the trial site.

At the conclusion or termination of this trial, trial site personnel and the CRA will conduct a final product supply inventory on the investigational drug accountability forms and all unused containers will be destroyed. Instructions for destruction of product will be provided to the site. The Clinical Trial Monitor will be supplied with a copy for filing of the investigational drug accountability forms. This documentation must contain a record of clinical supplies used, unused, and destroyed and shall include information on:

- All administered units
- All unused units
- All destroyed units (during the trial)
- All destroyed units at the end of the trial
- Date of destruction(s)
- Name and signature of the Investigator/pharmacist.

It must be ensured at each trial site that the trial treatment is not used:

- After the expiry date
- After the retest date unless the trial treatment is re-analyzed and its retest date extended.

This is to be closely monitored by the Clinical Trial Monitor.

6.9 Assessment of Investigational Medicinal Product Compliance

In this trial, subjects will receive trial treatment at the investigational site. Well-trained medical staff will monitor and perform the trial treatment administration. The information of each trial treatment administration including the date, time, and dose of trial treatment will be recorded on the eCRF. The Investigator will make sure that the information entered into the eCRF regarding drug administration is accurate for each subject. Any reason for noncompliance should be documented.

Noncompliance is defined as a subject missing > 1 study treatment administration for nonmedical reasons (see Section 5.5.1). If 1 study treatment administration is missed and the interval between the subsequent treatment and the last study treatment visit is longer than 4 weeks for nonmedical reasons, the criteria of insufficient compliance are met as well.

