5.5 Criteria for Subject Withdrawal

5.5.1 Withdrawal from Trial Therapy

Subjects will be withdrawn from trial treatment during the Induction and/or Maintenance Phase for any of the following reasons:

- Subjects meeting the definition of PD while on-treatment based on RECIST v1.1. Subjects in the Maintenance Phase receiving avelumab who experience disease progression may continue treatment with avelumab if they meet the criteria presented in Section 6.2.1 (Investigator believes the subject will experience clinical benefit from the treatment and there is no unacceptable toxicity resulting from the treatment [See Section 6.2.1]. Such subjects will be withdrawn from the treatment if there is a subsequent scan/assessment of PD based on RECIST v1.1).
- Significant clinical deterioration (clinical progression), defined as new symptoms that are deemed by the Investigator to be clinically significant or significant worsening of existing symptoms
- Unacceptable toxicity
- Withdrawal of consent
- Occurrence of an exclusion criterion, which is clinically relevant and affects the subject's safety, if discontinuation is considered necessary by the Investigator and / or Sponsor
- Therapeutic failure requiring urgent additional drug (if applicable)
- Occurrence of any Grade ≥ 3 ADRs or repetitive Grade 2 ADRs as defined in Section 5.1.3.2 for subjects receiving avelumab.
- Occurrence of AEs, resulting in the discontinuation of the trial drug being desired or considered necessary by the Investigator and / or the subject
- Occurrence of pregnancy
- Use of a nonpermitted concomitant drug, as defined in Section 6.5.2, where the predefined consequence is withdrawal from the trial drug
- Noncompliance (see Section 6.9).

For subjects receiving avelumab, if discontinuation occurs due to progression and a definitive diagnosis/radiographic confirmation is not made at the time of discontinuation, a second imaging scan may be allowed for confirmation of progression. If progression at the second imaging scan is not confirmed and the subject wishes to restart, the subject will be allowed to continue receiving avelumab as long as they meet the criteria for continuation of treatment beyond progression. For more information, see Section 6.2.1.

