Subjects will receive trial treatment until PD per RECIST v1.1, significant clinical deterioration (clinical progression), unacceptable toxicity, for the accepted maximal duration of the agent(s) selected, withdrawal of consent, or if any criterion for withdrawal from the trial or trial treatment is fulfilled.

Table 9 Allowed Therapy Regimens

Product Description	Dosage Form	Dose	Dosing Frequency
5-fluorouracil (5-FU)	Intravenous (IV)	Leucovorin 200 mg/m ² followed by 5-FU 2600 mg/m ²	On Day 1 every 2 weeks.
		Leucovorin 400 mg/m ² followed by 5-FU 400 mg/m ² intravenous push (IVP) followed by 2400 mg/m ² IV	Leucovorin on Day 1 5-FU IVP on Day 1 5-FU IV over 46-48 hours on Day 1 and Day 2
Capecitabine	Tablet	1000 mg/m ²	Twice daily for 2 weeks followed by a 1-week rest period, given in 3-week cycles
Oxaliplatin	Intravenous (IV)	85 mg/m ² with 5-FU	On Day 1 every 2 weeks
		130 mg/m ² with capecitabine	On Day 1 every 3 weeks. Capecitabine tablets should be swallowed with water within 30 minutes after a meal.

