The extent of exposure to randomized treatment (ie, avelumab or maintenance chemotherapy) will be characterized by duration (weeks), number of administrations, cumulative dose (eg, mg/kg or mg/m²), dose intensity (mg/kg/week or mg/m²/week), relative dose intensity (actual dose given / planned dose), number of dose delays, and number of infusion rate reductions (avelumab arm only), for the Safety-Maintenance Analysis Set. The number and percentage of non-compliant subjects (see Section 6.9) with regard to randomized treatment will be presented by treatment arm based on the Safety-Maintenance Analysis Set.

Prior Anti-Cancer Therapies and Procedures

Prior anti-cancer therapies (ie, anti-cancer medications other than trial treatment taken at any time prior to ICF signature) will be summarized using frequencies and percentages by drug class and preferred name within treatment arm and overall for the Safety-Induction Analysis Set and Safety-Maintenance Analysis Set. A similar summary will be provided by drug class, preferred name, and total subjects for the Safety-Induction Analysis Set. Prior anti-cancer procedures (ie, procedures undertaken at any time prior to ICF signature) will be listed only.

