### **Relative Dose Intensity**

The relative dose intensity (RDI) is defined as the actual dose intensity divided by the planned dose per cycle and expressed in %.

The summary of treatment exposure and compliance will be calculated for both Induction Phase and Maintenance Phase, and will include the following information:

- Duration of therapy (weeks)
- Total number of infusions received (avelumab and IV chemotherapy)
- Total number of Capecitabine doses received

The following will be included, broken down by separate chemotherapy treatment in the chemotherapy arm:

- Cumulative dose of therapy (mg/kg or mg/m^2)
  - Dose intensity (mg/kg/cycle) or (mg/m^2/cycle)
-

- Relative dose intensity of therapy categories: < 80%, 80% - < 90%, 90% - < 110%, >= 110%

A listing of treatment exposure and compliance will also be created to summarize the information listed above for each subject.

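### The fixed 4-week gap in Section 6.9 makes any single nonmedical missed visit non-compliance on the 3-weekly capecitabine control regimen, but not on the 2-weekly regimens when dosing is on target

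*Protocol*

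**What the plan says.** Protocol Section 6.9 has two triggers, both limited to nonmedical reasons. The first is more than one missed administration. The second needs only one miss with a long enough gap: "If 1 study treatment administration is missed and the interval between the subsequent treatment and the last study treatment visit is longer than 4 weeks". Neither is scaled to cycle length. The section also opens with the statement that "In this trial, subjects will receive trial treatment at the investigational site".

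The regimens differ in cycle length. Avelumab is infused every 2 weeks (Protocol 5.1.2.2.1). SAP Section 14 (Dose Intensity) uses 2-week cycles for avelumab and oxaliplatin + 5-FU, and 3-week cycles for oxaliplatin + capecitabine. Protocol Table 9 gives the capecitabine schedule as "Twice daily for 2 weeks followed by a 1-week rest period, given in 3-week cycles".

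The definition is used in two places. Protocol 5.5.1 lists non-compliance, by reference to 6.9, among the reasons for which subjects will be withdrawn from trial treatment. Protocol 8.5.6 plans a descriptive comparison: "The number and percentage of non-compliant subjects (see Section 6.9) with regard to randomized treatment will be presented by treatment arm". That figure is based on the Safety-Maintenance Analysis Set. SAP Section 14 gives no other definition of a non-compliant subject, and the single departure from the protocol listed in SAP Section 8 concerns a different matter.

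**The concern.** The rule fits a 2-weekly infusion but governs every regimen. A 2-weekly subject who misses one visit and returns on the target date sits exactly at 4 weeks, so the gap condition separates a prompt return from a late one. A 3-weekly subject who misses one visit is always past 4 weeks. For that regimen the gap condition separates nothing, and the count of more than one miss adds nothing for anyone who resumes treatment.

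Two things are at stake. One missed visit for a nonmedical reason meets a withdrawal criterion on one control regimen and may not on avelumab. And the by-arm percentage in 8.5.6 can show a difference that comes from cycle length rather than from behaviour.

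**Working it through.** The documents state no figure for this point, so there is none to reproduce. The check is calendar arithmetic.

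**Inputs.** Threshold: longer than 28 days (6.9). Cycle length c: 14 or 21 days (SAP Section 14). Visit window: -4/+2 days, with return to the target date after an off-schedule visit (Protocol 7.1.4). The last study treatment visit is read as the last visit at which treatment was given.

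**Gap after one missed visit, both doses on target: 2c.**
- 2-weekly: 2 x 14 = 28 days, not longer than 4 weeks, not flagged.
- 3-weekly: 2 x 21 = 42 days, flagged.

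**Gap with windows: 2c + b - a**, where a and b are the deviations of the last and next dose from target, each one of the 7 values from -4 to +2 (49 combinations).
- 3-weekly: 42 - 6 = 36 to 42 + 6 = 48 days; flagged in 49 of 49.
- 2-weekly: 28 - 6 = 22 to 28 + 6 = 34 days; flagged when b > a, that is in (49 - 7)/2 = 21 of 49.
- 2-weekly with the last dose on target: 24 to 30 days, flagged only at +1 or +2 days.

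**Illustration of the effect on a percentage.** The documents give no rate of nonmedical misses, so this is an assumption throughout: independent misses with probability p per administration, the same p in every regimen, 24 weeks of treatment (12 or 8 administrations), and treatment resumed after each miss.
- 3-weekly: 1 - (1-p)^8.
- 2-weekly on target: 1 - (1-p)^12 - 12p(1-p)^11.
- 2-weekly with all window combinations equally likely: the on-target value plus (21/49) x 12p(1-p)^11.

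| p | 2-weekly, on target | 2-weekly, windows | 3-weekly |
|---|---|---|---|
| 1% | 0.6% | 0.6 + 4.6 = 5.2% | 7.7% |
| 2% | 2.3% | 2.3 + 8.2 = 10.5% | 14.9% |
| 5% | 11.8% | 11.8 + 14.6 = 26.5% (from unrounded terms) | 33.7% |

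If a share s of treated controls is on capecitabine, the expected control-minus-avelumab difference is s times the gap between the 3-weekly and 2-weekly columns. At p = 2% and s from 0 to 1, that is 0 to 14.9 - 2.3 = 12.6 points on target, or 0 to 14.9 - 10.5 = 4.4 points with the windows.

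**The case against.** The best defence is that 6.9 limits calendar time off treatment. An avelumab subject with a 42-day nonmedical gap has missed two infusions and is non-compliant under the first trigger, so equal time between treatments is classified equally. That stands: a fixed interval is a legitimate choice and contradicts no other passage. It does not remove the effect on 8.5.6, where a control on capecitabine can be counted after one missed visit and an avelumab subject on target dates only after two.

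The SAP also does much of the work by cycle. Section 14 uses regimen-specific cycles, reports capecitabine doses received, keeps skipped capecitabine doses in the planned cycle dose and measures IV interruptions in cycles. Appendix I codes missed chemotherapy and missed avelumab doses for reasons other than an adverse event (INVPRO12, INVPRO13), with no 4-week condition. This makes correction easy, but none of it replaces the 8.5.6 figure.

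Four stronger readings are tempting and are not supported:
- A reader might infer that an avelumab subject always stays compliant after one miss. Late resumption within the permitted window can be flagged.
- A reader might infer a handicap on the whole control arm. Controls on oxaliplatin + 5-FU are treated exactly like avelumab subjects.
- A reader might infer that two missed capecitabine doses out of 28 in a cycle amount to non-compliance. Section 6.9 speaks of administrations performed by staff and of treatment visits; counting each home dose is strained.
- A reader might infer bias in the survival result. OS is analysed as randomized, subjects withdrawn from therapy are still followed for survival (5.5.1), and 6.9 non-compliance is not among the Per-Protocol exclusions in SAP Section 9. No rate is given from which any shortening of comparator treatment could be sized.

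**Conclusion.** The point holds as a minor one. For nonmedical misses, a single missed visit always meets the 6.9 definition on oxaliplatin + capecitabine once treatment resumes. On avelumab and oxaliplatin + 5-FU it does so only when the next dose falls later relative to its target than the last one did.

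The calendar result needs only the stated cycle lengths, window and threshold, and the natural reading of the last treatment visit. The figure of 21 in 49 counts combinations; treating it as a probability assumes uniform, independent use of the windows, which the documents do not state. The between-arm size cannot be fixed, because neither the capecitabine share nor the rate of nonmedical misses is given.

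The reach is limited to who meets the 5.5.1 criterion and to one descriptive by-arm figure. Randomization is complete (Protocol 8.1), so the reporting change carries most of the remaining value. Separately, the site-administration sentence in 6.9 does not describe tablets taken twice daily for 2 weeks.

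**What to change.** 1. **Reporting (8.5.6 and SAP Section 14).** Count nonmedical lapses in planned cycles of each subject's own regimen, so that one missed cycle means the same throughout. Show the control arm by regimen (oxaliplatin + 5-FU, oxaliplatin + capecitabine). Leave BSC-only subjects out of the denominator: they are in the Safety-Maintenance set, but SAP Section 14 excludes BSC from compliance calculations. Use the dosing data together with INVPRO12 and INVPRO13. The deviation codes are needed because the version 4.0 change list in SAP Section 4.1 says the collected data do not allow reasons to enter the calculation of interruption length. A reason other than an adverse event is close to, but not the same as, a nonmedical reason, and the table should carry a footnote saying so.

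2. **Wording (6.9 and 5.5.1).** These sections must be reconciled with the 3-weekly and oral regimens in Tables 3 and 9, including the statement that trial treatment is given at the site. Which rule applies is for the sponsor to decide.

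The cost is one reprogrammed table from data already collected, plus wording. The downside is that the control figure will no longer follow the literal 6.9 count.

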6.10 Blinding

This is an open-label trial; thus, trial treatment is not blinded.

6.11 Emergency Unblinding

Not applicable.

6.12 Treatment of Overdose

An overdose is defined as any dose \geq 10% over the calculated dose for that particular administration as described in this clinical trial protocol. Any overdose must be recorded in the trial treatment section of the eCRF.

For monitoring purposes, any case of overdose, whether or not associated with an AE (serious or nonserious), must be reported to the Sponsor's Global Drug Safety Department in an expedited manner using the appropriate reporting form (see Section 7.4.1.4).

There are no known symptoms of avelumab overdose to date. The Investigator should use his or her clinical judgment when treating an overdose of the trial treatment.

For all maintenance chemotherapy, Investigators must follow local institutional guidelines for overdose treatment.

6.13 Medical Care of Subjects after End of Trial

After a subject has stopped trial treatment, usual treatment will be administered, if required, in accordance with the trial site's SOC and generally accepted medical practice and depending on the subject's individual medical needs.

Upon withdrawal from trial treatment, subjects may receive the type of care they and their physicians agree upon. Subjects will be followed for survival and AEs as specified in Section 7.1.6.

7 Trial Procedures and Assessments

7.1 Schedule of Assessments

A complete Schedule of Assessments for the Screening period and the Induction Phase is provided in Table 1 and Table 2, for the Maintenance and Follow-up Phase in Table 3 to Table 6, and for CCI [REDACTED]

Prior to performing any trial assessments not part of the subject's routine medical care, the Investigator will ensure that the subject or the subject's legal representative has provided written informed consent according to the procedure described in Section 9.2.

7.1.1 Screening and Baseline Procedures and Assessments

The Screening procedures and Baseline assessments will be completed within 28 days before trial treatment starts.

During the Screening period and before any trial-related investigations and assessments are started, subjects will be asked to sign the ICF. The Screening procedures and Baseline assessments will be completed within 28 days of signing the ICF. Failure to establish eligibility within 28 days would result in screening failure and the subject will be excluded from the trial; however, subjects can be re-entered in the trial based on the Investigator's judgment and following Sponsor approval. In this case, a new ICF will be required to be signed by the subject.

The subjects' information that will be documented during Screening includes the demographic information (birth date, sex, and ethnicity) and the complete medical history, including the history of gastric cancer, previous and ongoing medications, and baseline medical condition (the information of concomitant medications and AEs and SAEs will be monitored throughout the trial treatment period). Moreover, an Emergency Medical Support card will be handed out at the Baseline assessments visit.

During Screening, subjects will undergo a complete physical examination, including recording body height and weight, vital signs, 12-lead ECG, and a determination of the ECOG PS (Table 1 and Table 2). The QoL questionnaires will be administered and completed by the subjects at baseline to collect baseline data about their health-related QoL.

The Screening laboratory examination includes hematology, hemostaseology, full serum chemistry, and full urinalysis (dipstick plus microscopic evaluation). Free thyroxine (T₄) and thyroid-stimulating hormone (TSH) will also be assessed at Screening for all subjects. The baseline CCI [REDACTED]

During Screening, a serum β -human chorionic gonadotropin (β -hCG) pregnancy test will be performed for females of childbearing potential (may be analyzed locally). HER2 testing (per local guidelines), blood HBV and HCV may be analyzed locally for all Screening subjects as these conditions are trial entry exclusion criteria (see Section 5.3.2). HBV surface antigen and anti-HCV tests must be performed at Screening to exclude subjects with hepatitis infection. If the anti-HCV

test is positive, the infection must be confirmed by an HCV RNA test. Females who are postmenopausal (age-related amenorrhea ≥ 12 consecutive months and increased follicle-stimulating hormone [FSH] > 40 mIU/mL), or who have undergone hysterectomy or bilateral oophorectomy are exempt from pregnancy testing. If necessary to confirm postmenopausal status, FSH will be drawn at Screening.

The tumor evaluation (type and staging, etc.) will be performed using CT scan or MRI (if MRI is used, CT of chest is mandatory) as well as tumor markers or any other established methods (see Section 7.2.5 for details). A brain CT/MRI scan is required at Screening if not performed within 6 weeks prior to entering the Induction Phase. A bone scan should be done at Screening as clinically indicated.

Subjects are required to provide tumor tissue samples; see Section 7.6.1 for details. Tumor tissue collection will be done of a recently-obtained biopsy within 6 months from a non-irradiated area, FFPE block containing tumor tissue or a minimum number of 10 (preferably 25) unstained tumor slides suitable for PD-L1 expression assessment (cut within 1 week). Criteria for determining the adequacy of tumor tissue are described in the Study Manual.

Subjects who undergo a biopsy specifically as part of the Screening assessments for this protocol shall be permitted to participate in the protocol provided they meet all other inclusion criteria and no exclusion criteria. It is recommended that multiple biopsy samples should be collected, as feasible, for biomarker assessment to minimize inaccuracies in assessment due to tumor heterogeneity. The site pathologist shall review the Hematoxylin and Eosin stains when more than one FFPE block from a subject has been received. If from a resection specimen, the block that maximizes tumor content and tumor cell preservation should be tested by the central laboratory. If from biopsy specimen(s), all available tumor-containing blocks representing up to a maximum of 6 distinct biopsies, should be sent to the central laboratory as feasible.

The blood samples for baseline CCI, and CCI as well as for CCI assessments (optional) will be collected before or on Day 1 before trial treatment starts for subjects randomly assigned to receive avelumab.

CCI

